9.6.1.1.6. Safety pause

Given that a) the homologous BNT162b2 vaccine schedule is licensed for use in 12 to 16 year-olds, b) Data from COMCOV2 demonstrates that BNT162b2 prime followed by NVXCoV2373 boost is no more reactogenic than homologous BNT162b2/BNT162b2 and c) employing fractional dose vaccines as the boost dose are expected to be less reactogenic than full dose regimens, there will be no planned safety pause or expedited review of reactogenicity data. Should significant safety concerns arise at any point (e.g. an AESI) then the DSMB will be consulted as appropriate.

9.6.1.2.

Subsequent visits

Follow-up visits will take place as per the schedule of attendances described in APPENDIX A: SCHEDULE OF PROCEDURES. Participants will be assessed for local and systemic adverse events, interim history, review of diaries (paper or electronic) and blood, saliva/ nasal fluid sampling performed at these time points as detailed in the schedule of attendances. Observations and physical exam will be performed as and when clinically indicated.

Vaccination procedures will be as for D0 visit, adapted to the specific vaccine being administered as outlined in the clinical study plan. Scheduling of the second vaccination visit (D56) should be mindful of any planned routine non-COVID-19 immunisation outside the study (e.g. seasonal influenza vaccine), to avoid administration of the study COVID-19 vaccine within a period 7 days before or after the planned routine vaccine. If necessary, in this situation scheduling of the D56 visit can be delayed beyond the specified D56 study window, but must not be brought forward to less than 8 weeks following D0.

If participants experience adverse events which the investigator (physician), CI and/or DSMB chair deem to require further close observation, the participant may be admitted to an NHS

hospital for observation and further medical management under the care of the Consultant on call.

9.6.2. Visits for participants receiving their first dose of COVID-19 vaccine in the community

The screening visit for these participants will include all the procedures for informed consent and eligibility assessment described above (section 9.6.1.1.1 and 9.6.1.1.2) including date of first dose of COVID-19 vaccination in the community.

The screening visit may be combined with the D56 visit, or be scheduled to occur separately, at some time before the D56 visit.

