11.7. Reporting procedures for Serious Adverse Events

In order to comply with current regulations on SAE reporting to regulatory authorities, the event will be documented accurately and notification deadlines respected. SAEs will be reported to members of the study team immediately the Investigators become aware of their occurrence, as described in the clinical study plan. Copies of all reports will be forwarded for review to the Chief Investigator (as the Sponsor's representative) within 24 hours of the Investigator being aware of the suspected SAE. The DSMB will be notified of SAEs that are deemed possibly, probably or definitely related to study interventions; the chair of DSMB will be notified immediately (within 24 hours) of the sponsor being aware of their occurrence. SAE/AESIs will not normally be reported immediately to the ethical committee(s) unless there is a clinically important increase in occurrence rate, an unexpected outcome, or a new event that is likely to affect safety of trial participants, at the discretion of the Chief Investigator and/or DSMB. In addition to the expedited reporting above, the Investigator shall include all SAE/AESIs in the annual Development Safety Update Report (DSUR) report provided for COM-COV, COM-COV2 and COM-COV3.

In participants who have received the NVXCoV2373 vaccine in this study, SAE's will be reported to Novavax according to the conditions and timelines outlined in the contemporaneous version of the Clinical Trial Agreement between Novavax and the University of Oxford University for conduct of this study.

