2. Exclusion of any other microbial cause, including bacterial sepsis, staphylococcal or streptococcal shock syndromes, infections associated with myocarditis such as enterovirus (waiting for results of these investigations should not delay seeking expert advice).
3. SARS-CoV-2 PCR testing may be positive or negative

AESIs should be collected and recorded in the AE reporting form in REDCap throughout the duration of this study. These should also be reported as SAEs if they fulfil the definition criteria for SAEs. All AESIs not already reported as SAEs should be included in the reports to the DSMB.

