11.13. Interim reviews

The safety profile will be assessed on an on-going basis by the Investigators. The CI and relevant Investigators (as per the trial delegation log) will also review safety issues and SAEs as they arise. The DSMB will evaluate safety data as required. The DSMB may also be consulted should safety concerns arise at any point.

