11.14. Safety holding rules

There will be no formal pausing rules given the extensive safety database for all vaccines used in this study.

The study can be paused upon advice of the DSMB, Chief Investigator, Study Sponsor, regulatory authority, Ethical Committee(s), for any single event or combination of multiple events which, in their professional opinion, jeopardise the safety of the participants or the reliability of the data.

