14.3.2. Safety Monitoring Committee

A Data Safety Monitoring Board (DSMB) will be convened. The DSMB will evaluate frequency of events, safety and efficacy data as specified in the DSMB charter. The DSMB will make recommendations concerning the conduct, continuation or modification of the study for safety reasons to the Trial Steering Committee.

The DSMB will review SAEs or AESIs deemed possibly, probably or definitively related to study interventions. The DSMB will be notified within 24 hours of the Investigators' being aware of their occurrence. The DSMB can recommend placing the study on hold if deemed necessary following a study intervention-related SAE.

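### Protocol sections 11.7, 11.10 and 14.3.2 together leave a serious AESI scored as unrelated with no explicit route to the DSMB, although a non-serious unrelated AESI has one

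*Protocol*

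**What the plan says.** Three sections of the protocol govern what the DSMB is sent.

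- Section 11.7, on SAEs: "The DSMB will be notified of SAEs that are deemed possibly, probably or definitely related to study interventions". The DSMB chair is told of these within 24 hours.
- Section 11.10, on AESIs: "These should also be reported as SAEs if they fulfil the definition criteria for SAEs". The next sentence reads: "All AESIs not already reported as SAEs should be included in the reports to the DSMB".
- Section 14.3.2, on the committee: "The DSMB will review SAEs or AESIs deemed possibly, probably or definitively related to study interventions".

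Other provisions give the DSMB broader access without fixing its content. Section 14.3.2 also says: "The DSMB will evaluate frequency of events, safety and efficacy data as specified in the DSMB charter". Section 11.13 says: "The DSMB will evaluate safety data as required". Section 9.6.1.1.6 says: "Should significant safety concerns arise at any point (e.g. an AESI) then the DSMB will be consulted as appropriate". Section 11.14 adds: "There will be no formal pausing rules given the extensive safety database for all vaccines used in this study".

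Under section 11.5 the reporting investigator assigns SAE causality. Under section 9.5 the staff who deliver the study know the arm.

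**The concern.** The sentence in section 11.10 reads as if every SAE already reaches the DSMB, so that only the remaining AESIs need to be added. Section 11.7 does not provide that, because it applies a relatedness filter. An AESI that is both serious and scored as unrelated is therefore taken out by each rule in turn.

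The filter is a case-by-case causality judgement, made by someone who may know the allocation. Some safety questions cannot be answered case by case. COVID-19 disease is a listed AESI in section 11.10, with particular attention to vaccine-associated enhanced disease. An individual hospitalised case has an obvious cause, the infection. Whether a schedule makes disease worse shows up in the number and severity of all cases in each arm. If cases scored as unrelated are left out, the DSMB lacks the data for that comparison, and an arm-aware filter could remove cases unequally between arms.

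**Working it through.** No arithmetic applies. The check classifies AESIs by seriousness and by causality score, then looks for a stated DSMB route for each combination. In the section 11.5 scale, 0 and 1 mean no or unlikely relationship, and 2 to 4 mean possible, probable or definite.

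| AESI | Section 11.7 (SAEs, related only) | Section 11.10 (AESIs not already SAEs) | Section 14.3.2 (related SAEs or AESIs) | Explicit route? |
|---|---|---|---|---|
| Serious, scored 2 to 4 | Yes | No, already an SAE | Yes | Yes |
| Non-serious, scored 2 to 4 | No, not an SAE | Yes | Yes | Yes |
| Non-serious, scored 0 or 1 | No | Yes | No | Yes |
| Serious, scored 0 or 1 | No, not related | No, already an SAE | No, not related | **None** |

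One combination of four has no named route. The third row also shows sections 11.10 and 14.3.2 disagreeing: one lists non-serious AESIs whatever their causality, the other limits AESI review to related events.

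**Can the fourth row be filled in practice?** Take hospitalised COVID-19.

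1. COVID-19 disease is an AESI (section 11.10).
2. Section 11.10.1 defines severe COVID-19 as hospitalisation, and inpatient hospitalisation meets the SAE definition in section 11.2. The case is therefore an SAE and drops out of the section 11.10 listing.
3. A score of 1 in section 11.5 requires three things jointly: unlikely timing, a likely alternative cause, and no known or plausible pattern of response to the product. Score 0 is also conjunctive. A case months after the boost, with proven infection, can meet all three. Follow-up runs to Day 236 post boost (Appendix A), and section 7.4 lets infected participants continue in the study.
4. The case then reaches the DSMB under none of the three sections. A mild, non-hospitalised COVID-19 case scored the same way would be listed under section 11.10.

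**Do the other channels close the gap?**

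- The Chief Investigator receives copies of all SAE reports within 24 hours (section 11.7), but acts there as the sponsor's representative and is not an independent monitor.
- Section 11.10.1 has COVID-19 cases examined for enhanced disease, but does not say that the DSMB receives them.
- Sections 9.6.1.1.6 and 11.13 leave DSMB consultation to discretion.
- Expedited SUSAR reporting (section 11.11) covers only suspected reactions.
- The Development Safety Update Report includes all SAEs and AESIs (section 11.7). It is annual, in a trial of about 10 months (section 7.2), and the DSMB is not among its listed recipients (section 11.12).
- Ethics committees are not normally told of these events immediately (section 11.7).
- The DSMB charter (section 14.3.2) may require fuller listings, but it is not shown.

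**The case against.** The best case for the protocol is that section 11.10 is only avoiding duplication, and that a working DSMB would receive tables of all SAEs under its charter. The remit in section 14.3.2 covers the frequency of events, which is hard to meet without such tables. This is plausible, and it may be what was intended. It does not change the fact that the protocol's own specific rules point the other way, and a site or safety team following the protocol text would be complying while omitting these events.

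It can also be said that the causality scale is set so that few events score 0 or 1. That stands, and it limits the point. A reasonable time relationship alone is enough for a score of 2.

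Three stronger readings are tempting, and the documents do not support them.

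- A reader might infer that the DSMB is the only body that can halt the study. Section 11.14 names five sources of advice on which it can be paused: the DSMB, Chief Investigator, sponsor, regulatory authority and ethics committees. The DSMB itself makes recommendations to the Trial Steering Committee.
- A reader might infer that the DSMB would never learn of these events. The discretionary routes and the charter mean that it may; what is missing is an explicit rule.
- A reader might infer that myocarditis soon after a BNT162b2 boost would be hidden. Section 11.8.1.1 lists myocarditis as an expected serious reaction to that vaccine, so it could hardly be said not to follow a known pattern. It should be scored at least possible and go to the DSMB chair within 24 hours.

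**Conclusion.** The point holds as an internal inconsistency with a specific consequence: serious AESIs scored 0 or 1 have no explicit route to the DSMB, while less serious events with the same score do. It bears mainly on later events and on those attributed to infection, with hospitalised COVID-19 as the clearest example. Serious AESIs judged related are properly covered.

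Its size is one cell of four in the reporting rules. It cannot be turned into an expected number of missed events, because the protocol gives neither a rate of serious AESIs nor the share that would be scored as unrelated, and any such figure would be invented. The conclusion assumes that the three sections are applied as written and that the charter does not override them. The concern about an arm-aware filter further assumes that the reporting investigator is among the staff who know the allocation; section 9.5 makes this likely but does not state it for that role. It is worth correcting, because the participants are adolescents, some on unapproved schedules, and there is no formal pausing rule to act as a second safeguard.

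**What to change.** Reconcile sections 11.7, 11.10 and 14.3.2. In section 11.10, state that all AESIs, whether or not they have also been reported as SAEs and whatever their causality score, are included by arm in the reports to the DSMB. Word sections 11.7 and 14.3.2 so that the relatedness condition governs the 24-hour notification only and does not limit what the periodic reports contain. Keep that 24-hour notification for related events as it is, and check that the DSMB charter says the same.

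The cost is a few sentences in three sections and some additional lines in an existing report. SAEs and AESIs are already sought at every study visit (section 11.6.2), so no new data collection or committee is needed. The small downside is that the DSMB will receive some events that prove to be unrelated.

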11.10.1. Disease enhancement following vaccination

Severe COVID-19 disease will be defined as hospitalisation, with further grading of severity according to the WHO ordinal scale (June 2020).(23) Cases of COVID-19 disease will be examined for the possibility of vaccine associated enhanced disease (VAED). This will be evaluated on the basis of the most recent recommendations of the Brighton Collaboration. Detailed clinical parameters will be collected from medical records and aligned with agreed definitions, as they emerge. Investigations will be defined by the laboratory analysis plan.

11.11. SUSAR reporting

All SUSARs will be reported by the sponsor delegate to the relevant Competent Authority and to the REC and other parties as applicable. For fatal and life-threatening SUSARS, this will be done no later than 7 calendar days after the Sponsor or delegate is first aware of the reaction. Any additional relevant information will be reported within 8 calendar days of the initial report. All other SUSARs will be reported within 15 calendar days.

Principal Investigators will be informed of all SUSARs for the relevant IMP for all studies with the same Sponsor, whether or not the event occurred in the current trial.

11.12. Development Safety Update Reports

A Development Safety Update Report (DSUR) will be prepared annually, reporting on this study, 'Comparing COVID-19 Vaccine Schedule Combinations (Com-COV) (Ethics Ref: 21/SC/0022, IRAS Project ID: 291055) and Comparing COVID-19 Vaccine Schedule Combinations -stage 2 (Com-COV2)(Ethics Ref: 21/SC/0119, IRAS Project ID 297443), within 60 days of the anniversary of the MHRA approval for the 'first' COMCOV study. The DSUR will be submitted by the CI to the Competent Authority, Ethics Committee, HRA (where required), Host NHS Trust and Sponsor.

11.13. Interim reviews

The safety profile will be assessed on an on-going basis by the Investigators. The CI and relevant Investigators (as per the trial delegation log) will also review safety issues and SAEs as they arise. The DSMB will evaluate safety data as required. The DSMB may also be consulted should safety concerns arise at any point.

11.14. Safety holding rules

There will be no formal pausing rules given the extensive safety database for all vaccines used in this study.

The study can be paused upon advice of the DSMB, Chief Investigator, Study Sponsor, regulatory authority, Ethical Committee(s), for any single event or combination of multiple events which, in their professional opinion, jeopardise the safety of the participants or the reliability of the data.

11.15. Contraception and pregnancy

11.15.1. Contraception

Post-menarchal female participants are required to use an effective form of contraception from enrolment continuously until three months after boost immunisation.

Acceptable forms of contraception for volunteers of female sex include:

- Established use of oral, injected or implanted hormonal methods of contraception
- Placement of an intrauterine device (IUD) or intrauterine system (IUS)
- Total hysterectomy
- Bilateral Tubal Occlusion
- Barrier methods of contraception (condom or occlusive cap with spermicide)
- Male sterilisation, if the vasectomised partner is the sole partner for the subject
- True abstinence, when this is in line with the preferred and usual lifestyle of the subject (Periodic abstinence and withdrawal are not acceptable methods of contraception)

11.15.2. Pregnancy

Should a participant become pregnant during the trial, no further study IMP will be administered. They will be followed up for clinical safety assessment with their ongoing consent and in addition will be followed until pregnancy outcome is determined. We would not routinely perform venepuncture in a pregnant participant unless there is clinical need.

12. STATISTICS

12.1. Sample size

The total sample size of this trial will be up to 270 Since the primary endpoint analysis will be descriptive and therefore no formal sample size calculation is carried out to determine the sample size of the trial. The number has been therefore chosen based on practical constraints. The precisions on estimating the systematic reactions based on 90 per arm are:

True event rate	Precision (normal approximation)	95% exact binomial CI
5%	±4.5%	1.5%-11.7%
10%	±6.2%	4.7%-18.1%
25%	±8.9%	16.5%-35.2%
50%	±10.3%	39.3%-60.7%

For secondary endpoints of immunogenicity, the minimum geometric mean ratios that can be detected with 90% power at two-sided 0.05 based on 90 per arm are:

Standard deviation on log10 scale	Minimum GMR to detect
0.4	1.57 (or 0.64)
0.5	1.75 (or 0.57)
0.6	1.96 (or 0.51)

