Accordingly, this study will determine the side effect profile, and the immune responses of heterologous and/or fractional COVID-19 vaccination schedules in adolescents, using BNT162b2 as a first dose, and a second dose administered from 8 weeks later of either BNT162b2 (full or one third dose) or NVXCoV2373 (full dose). Following the JCVI recommendation on 29th November 2021 that all 12 to 15 year-olds should be offered a second dose of BNT162b2 vaccine, the study design was amended to focus on immune response to BNT162b2. After this date, participants will be randomised 1:1 to either full or one-third dose BNT162b2 for their second vaccination. Participants will no longer be randomised to the Novavax arm of the study to prioritise the arms of the study that are likely to be more policy relevant. This does not reflect any concern regarding the safety or immunogenicity of the Novavax vaccine. A further review of the study design will be undertaken following an interim analysis in late 2021, and with input from the study Trial Steering Committee.

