7.3. Study groups

A total of up to 270 (+ up to an additional 10%) participants will be enrolled and randomised (1:1:1) as below:

Group	Arm	Prime (Day 0)	Boost (day 56)
	1	BNT162b2	BNT162b2
	2	BNT162b2	BNT162b2 (one-third dose)
	3	BNT 162b2	NVXCov2373

After 29th November 2021, the enrolment of participants who have received their first dose of COVID-19 vaccine in the community will be temporarily suspended. Only participants who have received their first dose of COVID-19 vaccine in the study will be randomised to a second dose. They will be randomised (1:1) as below:

Group	Arm	Prime (Day 0)	Boost (day 56)
	1	BNT162b2	BNT162b2
	2	BNT162b2	BNT162b2 (one-third dose)

Randomisation will be performed at the time of the second dose, and stratified by study site and anti-nucleocapsid IgG status at baseline where available.

The study will be single-blind, i.e. while staff involved in study delivery will be aware of what vaccine schedule the participant is receiving, the participant themselves will remain blinded to their boost vaccine. This blind will be maintained by applying a masking tape over the vaccine syringe as detailed in the study clinical study plan. Laboratory staff will also be blinded to the vaccine schedule received.

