9.4. Randomisation

Computer generated randomisation list will be prepared by the study statistician. Participants will be randomised 1:1:1 to the three study groups. After 29th November 2021, participants will be randomised 1:1 to the two study groups.

Participants will be randomised using block randomisation. Random block sizes of 3 and 6 will be used before 29th November 2021, and random block sizes of 2 and 4 will be used after 29th November 2021. Randomisation will be performed at the time of the second dose, and stratified by study site and anti-nucleocapsid IgG status at baseline (where available).

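### Section 12.1 still assumes 90 participants in each of three arms, although Novavax allocation has stopped; its Novavax precision and power figures are probably too favourable, by an amount the protocol does not let a reader work out

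*Protocol*

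**What the plan says.** Section 12.1 sets the size: "The total sample size of this trial will be up to 270". The number rests on practical constraints, and the primary analysis is declared descriptive. Two tables follow. The first gives the precision of an event rate: "The precisions on estimating the systematic reactions based on 90 per arm are" ±4.5, 6.2, 8.9 and 10.3 points at true rates of 5, 10, 25 and 50%. The second concerns immunogenicity: "the minimum geometric mean ratios that can be detected with 90% power at two-sided 0.05 based on 90 per arm are" 1.57, 1.75 and 1.96 at log10 standard deviations of 0.4, 0.5 and 0.6.

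The 90 comes from the allocation in section 7.3: "A total of up to 270 (+ up to an additional 10%) participants will be enrolled and randomised (1:1:1) as below".

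That allocation was then changed. Section 2 says: "Participants will no longer be randomised to the Novavax arm of the study". Section 9.4 says: "After 29th November 2021, participants will be randomised 1:1 to the two study groups". Section 7.3 adds that after the same date "the enrolment of participants who have received their first dose of COVID-19 vaccine in the community will be temporarily suspended", so only participants primed in the study are randomised from then on.

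Section 12.2 still plans a GMR for each heterologous arm against the homologous arm, and comparisons of reaction rates between arms by Fisher's exact test. Section 12.4 describes the redesign and says that recruitment and sample size will be reviewed after the December 2021 analysis. No section gives the number randomised to Novavax before the change, or a new target for any arm.

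**The concern.** The tables in 12.1 are the protocol's only statement of how precisely it can estimate reactogenicity and what immunogenicity differences it can detect. They describe three arms of 90, whereas the current design has two arms that continue to fill and one closed at an unreported number.

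The outdated figure bears on Novavax, the only arm with a different boost vaccine and so the arm closest to the primary objective of heterologous-boost reactogenicity. A reader of 12.1 would credit the Novavax comparison with 90% power at a GMR of 1.75 (SD 0.5), and might read an inconclusive Novavax result as stronger evidence of similarity than it is.

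The text was revised after the change: a footnote in section 11.10 cites an investigator's brochure addendum of 11 January 2022. By then the Novavax number was fixed and could have been stated.

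**Working it through.** **Inputs.** Total up to 270, or 297 with the extra 10% (7.3); 1:1:1 until 29 November 2021, then 1:1 without Novavax (7.3, 9.4); 90% power, two-sided 0.05, log10 SD 0.4 to 0.6 (12.1). The Novavax number k is not given and is an assumption throughout.

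**Step 1: reproduce the stated figures at n = 90.**
- Half-width = 1.96 × √(p(1−p)/n). At p = 0.50: 1.96 × √(0.25/90) = 10.3 points. The other rates give 4.5, 6.2 and 8.95 points, and the exact intervals also match.
- Detectable GMR = 10^(d × SD), where d is the standardised difference at which a two-sample t-test has 90% power. For 90 versus 90 this gives 1.56, 1.75 and 1.96. Power at the stated ratios is about 90%, so the printed 1.57 is a rounding matter.

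The arithmetic is sound at 90.

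**Step 2: what the amended allocation delivers.** If k were randomised to Novavax, about 3k had been randomised when that arm closed. Arms 1 and 2 finish with (N − k)/2 each.
- N = 270: k = 90 requires 3 × 90 = 270 already randomised, leaving nobody for the 1:1 stage. Any 1:1 randomisation therefore means k < 90.
- N = 297: k = 90 is possible only if about 270 were randomised 1:1:1 first, leaving 27 for the 1:1 stage.
- Arms 1 and 2 with N = 270: (270 − k)/2 is at least 90 whenever k is at most 90.

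**Step 3: Novavax figures for assumed k, N = 270, SD 0.5.** Concurrent controls means k versus k. All controls means k versus (270 − k)/2.

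| k | Half-width at 50% | 90%-power GMR, concurrent | 90%-power GMR, all | Power at 1.75, concurrent | Power at 1.75, all |
|---|---|---|---|---|---|
| 30 | ±17.9 | 2.66 | 2.15 | 46% | 66% |
| 50 | ±13.9 | 2.13 | 1.90 | 67% | 81% |
| 60 | ±12.7 | 1.99 | 1.84 | 75% | 85% |
| 80 | ±11.0 | 1.81 | 1.77 | 86% | 89% |
| 90 (stated) | ±10.3 | 1.75 | 1.75 | 90% | 90% |

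Hand check at k = 50 by the normal approximation, 10^[(1.96 + 1.2816) × 0.5 × √(1/n₁ + 1/n₂)]: 50 versus 50 gives 10^(3.2416 × 0.5 × 0.200) = 2.11; 50 versus 110 gives 10^(3.2416 × 0.5 × 0.1706) = 1.89. Both are close to the t-based 2.13 and 1.90.

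**Step 4: the 297 ceiling.** The half-widths depend only on k and do not change. With all controls and k = 80, arms 1 and 2 hold 108.5 on average and power at 1.75 is 91%, so the stated ratio is then met. With k = 60 it is 86%.

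**Step 5: one-third versus full dose, N = 270, SD 0.5.** k = 30, 50, 60 or 80 leaves 120, 110, 105 or 95 per arm and a detectable GMR of 1.62, 1.66, 1.68 or 1.72, all better than the stated 1.75.

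**The case against.** The strongest reply is that little turns on these tables. The primary analysis is descriptive, the size was set on practical grounds, no decision rule uses the figures, reported confidence intervals will reflect the numbers actually enrolled, and 12.4 promises a review of sample size. This stands, and it limits the consequence. It does not make the printed figures describe the current design, and a later review does not correct them.

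Four stronger readings are tempting and are not supported:

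- **That the trial as a whole cannot reach 90 per arm.** The two BNT162b2 arms have at least 90 each if 270 is reached, and theirs is the comparison on which the amended design focuses. They would fall short only if total recruitment did; for example, 60 per arm would give a detectable GMR of 1.99. The suspension of community enrolment is called temporary, and no section projects a shortfall.
- **That 90 in the Novavax arm is strictly impossible.** The extra 10% leaves room for it, if about 270 had been randomised before the change.
- **That the Novavax loss is known to be large.** It is large at k = 30 and slight at k = 80, and the protocol does not say which applies. The concurrent-control figures are the more severe, and section 12.2 does not restrict controls to concurrent ones. There is a good argument for doing so, because later controls are all study-primed and were never randomised against Novavax. That remains a design choice, so both sets are shown.
- **That omitting the precision of a between-arm risk difference is an error.** Single-arm precision fits a descriptive primary analysis, and the planned comparison is Fisher's exact test. Adding a risk difference would be a preference.

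**Conclusion.** The point holds as an internal inconsistency: the per-arm number in 12.1 was not updated when 7.3 and 9.4 closed the Novavax arm. With a total of 270, the direction is certain once anyone is randomised 1:1: wider intervals, a larger detectable ratio, and less than 90% power at the ratio of 1.75. With a total of 297 the half-widths are still too narrow unless about 270 were randomised before the change, but the stated GMR can be met if k is near 80 and all full-dose controls are used.

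The size cannot be fixed from the protocol. Over an assumed k of 30 to 80 with 270 in total and SD 0.5, power at 1.75 runs from 46 to 86% with concurrent controls and from 66 to 89% with all controls. The half-width at a 50% event rate runs from ±17.9 to ±11.0 points. The concurrent figures assume that 1:1:1 blocks gave about equal numbers in the three arms before the change, and none of these figures allows for missing samples or diaries.

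The consequence is moderate, given a descriptive primary analysis. The figures for one-third versus full-dose BNT162b2 stand, or are conservative, if 270 is reached.

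**What to change.** In section 12.1, replace the single figure of 90 per arm with the number actually randomised to Novavax by 29 November 2021 and the projected size of each BNT162b2 arm. State whether the projection uses 270 or 297. Give the event-rate precision for each arm at its own size. Give the detectable-GMR table twice: once for one-third versus full dose, and once for Novavax versus full dose, stating whether the controls are those randomised concurrently or all full-dose participants. Section 12.2 should use the same definition of controls.

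The cost is about half a page. No extra enrolment and no change to trial conduct is needed. The Novavax figures will probably look less favourable, and those for the BNT162b2 comparison may look better.
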